3.2.4 Management plan

Milestones

MS1	User interfaces implemented for FriWalk and social network
MS2	Ethical approval granted
MS3	Collaboration with museums finalised
MS4	Walkers shipped to UK
MS5	Implementation of system in museum environment
MS6	Completed workshop via FriTab API
MS7	Completed social network testing
MS8	Completed tour testing
MS9	Data analysis
MS10	Post-trial presentation and discussion with participants

Risk management

There are some risks associated with the proposed plan and most of these are consistent with the risks identified in the clinical testing. However, some unique risks are identified below.

Table 11. Risk management

Risk	Description	Likelihood	Threat	Strategy
1	Not receiving user interfaces designed for older adults	Possible	Low	If user interfaces designed for older adults specifically are not implemented, we will have to use whatever interfaces are available. These may not be very user- friendly but we will endeavour to explain them as much as possible to users and familiarise them with the UIs. We will also provide as much assistance as necessary and let them know that we are available to help.

2	Museums do not agree to collaborate	Unlikely	Significant	If no museums agree to collaborate (although some have agreed in principle) or they restrict the collaboration in some way, we may have to use facilities at UNAN to provide a "mock" museum or something similar.
3	Insufficient activities are available for participants via the social network	Unlikely	Major	Experimenters will design activities and actively seek out collaborators to provide activities.

3.2.5 Data Management plan

Data will be collected from the social network system, from questionnaires and from the FriWalk sensors. These data will be stored in an Access database to facilitate matching of participant data and easy retrieval. It will be available to partners in the project but will not be made open access due to the project-specific nature of the data. However, the data will be available on request to enable scrutiny.

3.2.6 Plan for statistical analysis

A variety of statistical methods will be used to analyse the data. Regression analysis will be used to model the effects of using the social network system (acceptance of recommendations) on outcome measures such as social and physical activity. This will allow other measures such as attitudes to the system or engagement with the system to be controlled for.

ANOVA (analysis of variance) tests will be used to assess differences between groups in the CPSN (social network users vs. non-users and pre-trial vs. post-trial) and in the FriWalk testing (experimental groups vs control groups). These will also allow for the testing of interaction effects to see whether the use of the walker interacts with other measures (e.g. fear of falling or frailty) on the effects of the intervention (such as increased confidence or increased physical activity).

4 Ethical approval

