3.2.3.1 Objectives

Broadly speaking, there are two objectives for both the CPSN and the FriWalk. The use of both should increase both (1) *social involvement* and (2) *physical activity*. There are several other objectives listed below, and the two key objectives are broken down into more detail below.

Controlled factors

While there are clear objectives around what we want the system to achieve, these will be affected by several interacting variables such as the user's perception of the system's ease-of-use, their enjoyment of the system and their sense of the usefulness of the system. These variables are drawn from the Unified Theory of Acceptance and Use of Technology (UTAUT) (Morris, Hall, Davis, Davis, & Walton, 2003) and we expect that a user's perception of the system's ease-of-use (for example) will affect the benefits that they gain from using it; if they find it hard to use they are less likely to adopt recommendations or find it helpful. These control variables apply both to the FriTab API and to the FriWalk (i.e. two sets of questions). While we treat them as control variables, we also expect to see some changes in the levels of enjoyment and sense of usefulness. Increasing use should, hopefully, increase these levels. The variables we will measure are:

- 1. Performance expectancy Perception of the extent to which the system will be/is useful.
- 2. Effort expectancy Perception of the extent to which the system will be/is easy to use.
- 3. Attitude towards the system positive or negative view of the system.
- 4. Social influence Perception of the extent to which other people like or dislike the system.
- Facilitating conditions Perception of the extent to which someone helps in getting used to the system.
- 6. Self-efficacy Perception of the extent to which the user can use the system by themselves (aided or unaided).
- Anxiety Perception of the extent to which the system makes one feel anxious when using it (e.g. fear of making mistakes).
- Intention to use the system The extent to which the user says they would use the system again.
 This is a clear outcome measure that expresses overall intention to use the system.

Outcome measures (social network)

There are several general objectives and accompanying specific objectives.

Firstly, for the testing of the *CPSN*:

- 1. Social involvement

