 - a. Perceived social involvement: this should increase as a result of using the system, but will interact with the user's extent of use of the system. The more they use it, the more

benefits they will receive. Those who do not engage much with the system are not expected to show benefits.

- b. Actual social involvement: by using participant diaries, we will show the effect of using the social network on actual involvement.
- c. Quality of recommendations: the more that a user discloses to the system, the greater the quality of the recommendations.
- d. Turnout to event: users who are more engaged with the system and who perceived higher quality of recommendations will be more likely to attend an event to which they are invited. This event will be organised by the experimenters and numerous people will be invited.
- e. Liking of the participants: At the event, liking for each other will be greater depending on the number of similar interests as recorded by the system compared to groups whose members have been randomly selected (similarity-attraction hypothesis; Byrne, 1972).
- 2. Physical activity
 - a. Number of steps taken: as a result of being more socially involved and attending an event, participants should show an increased number of steps compared to their own pattern of activities in a similar period without the intervention. They will also show more steps compared to a control group who do not take part in the intervention.
- 3. General well-being
 - a. Well-being: as a result of having more physical activity, users should show increased levels of subjective well-being (Netz et al. 2005).
 - b. Perceived sleep quality: this should increase as a result of having more physical activity. We know that sleep quality is affected by physical activity (King et al. 1997; Sherrill, Kotchou, and Quan 1998) and that sleep is linked to poor health outcomes (Strine and Chapman 2005). Therefore, it is an important finding if physical activity can increase sleep quality through use of the ACANTO system.

Outcome measures (FriWalk)

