3.2.3.4 Protocol

There are two use cases matching the testing of the two different aspects of the system: the CPSN and the FriWalk itself. These are described below.

Use case 1: Using the social network

George is an elderly man who lives alone. While he sometimes finds out what is going on in the area, he would like to know about more events. When he is offered a chance to use the ACANTO CPSN, he is eager to try it. He enters his details into the FriTab API and will be presented with some recommendations. He finds one that he likes and decides to try it. The next day, he attends the recommended activity. His step counter records his physical activity and it can be seen that his physical activity has increased. At the event, he also meets several people and feels more socially involved as a result.

Use case 2: Using the FriWalk

Sandra is an elderly lady who lives alone. She has some difficulties with walking after having a fall several months ago. One day, she is invited to attend a session at the museum where she will use the FriWalk to get a guided tour. She decides that she will attend because the subject of the tour matches her interests. At the museum, she meets several other people who have come for the tour. A guide shows them how to use the FriWalk and they have a chance to ask any questions. After seeing how her FriWalk works, Sandra sets off with some other users. They take a tour about "The history of the North-East of England" and the FriWalk shows them where to go. At one point, Sandra decides that she needs to use the toilet. She presses a button requesting guidance to the toilet and the FriWalk shows her where to go. After returning from the toilet, the FriWalk guides her back to the group. At the end of the tour, Sandra is impressed with the system and decides to come back and try it again. She enjoyed using it and appreciated the interaction with other people in the group as they explored the features of the system.

Recruitment process (social network study)

Participants will be recruited from several sources: some participants are already engaged with longitudinal tracking for the ACANTO project, while others will be recruited fresh.

- 15 participants will be recruited from existing participants (i.e. longitudinal tracking, Task 1.2.4).
- 15 participants will be recruited from outside existing participants.
- 15 participants will be selected as controls (they will not use the social network).

Recruitment process (FriWalk study)

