Sense of common identity	Two items adapted from Drury, Cocking, & Reicher, (2009) asking about a sense of unity within groups.	
Well-being	Personal wellbeing index (International Wellbeing Group 2013)	
Time taken to find facilities	Comparison of time taken between participants who do not use the FriWalk to find facilities and those who do use it (given unfamiliarity with the environment).	
Sleep quality	Pittsburgh Sleep Quality Index (Buysse et al. 1989)	
Willingness to return	Several items asking about whether the participant would come back to the museum for a similar tour using the FriWalk.	

Phases

The following is a brief outline of the phases involved in collecting data for the social network trial.

Table 9. Phases of social network study

Phase 1: Ethics and Recruitment			
Ethical approval	Ethical approval forms should be completed and approved		
Recruitment	Recruitment of 30 participants and invitation to try the system.		
	Phase 2: Pilot study		
Seeding system with	Experimenters will add activities to the system from the surrounding area and		
recommendations	will tag these appropriately.		
Checking system	Experimenters and some participants will check that the system is working		
	properly.		
	Phase 3: Testing		
Initial workshop	Participants will be invited to a workshop where the system will be explained		
	to them and where they will enter their data. At this initial session,		
	participants will be given a diary to complete during the next 2 weeks. The		

	diary will contain questions about their social involvement. They will also be given step counters and will also be asked to complete a short questionnaire for baseline measurement. For practical purposes, this workshop may be split into two or three workshops (given participant availability).	
Using the network	Participants will use the FriTab API for a period of 2 weeks.	
Control group	An additional 15 participants (control group) will be asked to complete diaries and carry step counters for 2 weeks.	

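### The social-network study promises to compare users' steps with their own pre-use activity, but Table 9 schedules no pre-use period, and the comparisons that remain are open to bias

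*Protocol*

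**What the plan says.** Section 3.2.3 of the protocol announces two tests of the social network: users against their own earlier state, and users against people who do not take part. Section 3.2.3.1 makes the first one concrete for steps: "participants should show an increased number of steps compared to their own pattern of activities in a similar period without the intervention". Section 3.2.6 plans an ANOVA of users against non-users and of before against after the trial.

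The data to be collected are set out in Section 3.2.3.4, Table 9. At the first workshop the system is explained, users enter their details and receive a diary for the following 2 weeks, and "They will also be given step counters and will also be asked to complete a short questionnaire for baseline measurement". Use of the network then lasts 2 weeks. For the comparison group, "An additional 15 participants (control group) will be asked to complete diaries and carry step counters for 2 weeks". The recruitment list adds: "15 participants will be selected as controls (they will not use the social network". Of the 30 users, 15 come from the longitudinal tracking of Task 1.2.4 and 15 are new.

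The first model in Section 3.2.6 is described thus: "Regression analysis will be used to model the effects of using the social network system (acceptance of recommendations) on outcome measures". On covariates it continues: "This will allow other measures such as attitudes to the system or engagement with the system to be controlled for". Of the technology-acceptance variables, Section 3.2.3.1 says: "While we treat them as control variables, we also expect to see some changes in the levels of enjoyment and sense of usefulness". It goes on: "Increasing use should, hopefully, increase these levels".

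**The concern.** The objective and the schedule do not fit together. A comparison with a person's own activity needs a recorded stretch of activity before the system is introduced, and Table 9 has none. A later analysis plan cannot supply data that were not collected. Steps are the only physical-activity measure in Table 7, and physical activity is one of the study's two key objectives. Diary-recorded social involvement has the same gap.

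Without that comparison, the claim about steps rests on two others. One sets users against controls who are selected and have no pre-use value. The other regresses activity on how many recommendations a user chose to accept. More active or sociable people may accept more recommendations and walk more in any case. If the covariates are measured after use, adjusting for them takes away part of the effect being sought.

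More than this one study is at stake. Section 3.2.1 leaves the combined clinical and social use untested, on the ground that success at both ends lets it be assumed to some extent. That argument needs a credible effect from the social study.

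**Working it through.** **Head count.** 15 + 15 = 30 users, which reproduces the figure in Table 9, and 30 + 15 = 45 in all. The protocol gives no power, SD or effect size for this study. The two-sided 5% level used here is an assumption, and results are in SD units.

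**What is recorded, and when (Table 9).**

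| Measure | Users, before | Users, during or after | Controls, before | Controls, during or after |
|---|---|---|---|---|
| Steps | none scheduled | 2 weeks | none scheduled | 2 weeks |
| Diary contacts | none scheduled | 2 weeks | none scheduled | 2 weeks |
| Questionnaire | at workshop | at return | not stated in the control row | return row covers everyone |

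Table 10 does schedule diaries and counters for baseline activity, but only for the museum study of the FriWalk.

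**During-use comparison of steps, true effect zero.** Let g be the gap in usual activity between the groups. The expected difference is then g, not zero. Its standard error is sqrt(1/30 + 1/15) = sqrt(0.10) = 0.316 SD.

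- g = 0.2: 0.2/0.316 = 0.63 standard errors. A t test rejects with probability 0.095 (0.097 in 20,000 simulated studies).
- g = 0.5: 0.5/0.316 = 1.58. Probability 0.340 (simulated 0.338).
- g = 0.8: 0.8/0.316 = 2.53. Probability 0.696 (simulated 0.692).
- g = 0: simulated 0.049, as it should be.

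**The same with a pre-use value.** With an assumed correlation of 0.7 between the two periods and a gap that is stable over time, a test on change scores rejects in 0.046 to 0.052 of simulated studies over the four gaps. Under the same model, covariate adjustment for the pre-use value (ANCOVA) leaves a bias of (1 − 0.7) × g, that is 0.06, 0.15 and 0.24 SD. Both improve on 0.2, 0.5 and 0.8 SD, but they rest on different assumptions.

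**Regression on acceptance (large-sample fits, assumed coefficients).**

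- Self-selection, no true effect: a trait that correlates c with both acceptance and steps gives an unadjusted slope of c × c. This is 0.3 × 0.3 = 0.09 or 0.5 × 0.5 = 0.25, where the truth is 0.
- Post-use attitude as covariate, no confounding: a total effect of 0.30 direct + 0.20 through attitude = 0.50 is estimated as 0.30. If all 0.50 runs through attitude, the estimate is 0.00.
- The two problems interact. When attitude was also allowed to reflect the trait, adjusting for it moved the false slopes from 0.09 and 0.25 to −0.03 and 0.04. The same adjustment that reduces self-selection bias also removes real effect, and the net result depends on coefficients that nobody knows.

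**The case against.** A fair defence has five parts.

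- **Attitudes.** The plan does not say whether attitudes enter as pre-use or post-use scores. Pre-use scores are legitimate covariates, and the choice could be left to an analysis plan. Section 3.2.3.1 expects only enjoyment and sense of usefulness to change, and it says so as a hope. A reader might infer that it also expects use to raise engagement, but it does not say so. Section 3.2.3.4 adds engagement in order to allow for less interested participants. That answers part of the point. The warning about lost effect applies only to post-use scores, and the difficulty with engagement is its close overlap with acceptance.
- **Control questionnaires.** It is tempting to conclude that controls have no baseline questionnaire and that the before-and-after ANOVA is missing a cell. Table 9 is only a brief outline, and its last row has everyone return for a questionnaire that measures change from the start of the study. This can be read to include controls. It is an ambiguity to clear up.
- **Earlier data.** The 15 tracked users may have step data from Task 1.2.4, and Section 3.2.3.1 draws on that task's questionnaires for fear of falling in the FriWalk study. The protocol does not say that the task holds steps and plans no use of them here. They would not cover the 15 new users. Nor does the text show that every tracked participant becomes a user, since it does not say how many there are or where controls come from.
- **Group ANOVA.** The users against non-users comparison does not condition on acceptance, engagement or attitudes, so it can be estimated if the groups are comparable.
- **Sizes.** All gaps and coefficients above are assumed, and the 0.09 and 0.25 slopes belong to an unadjusted fit, which is not what is planned.

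None of this supplies a pre-use period for steps or diaries, or a reason to take selected controls as comparable.

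**Conclusion.** The point holds for steps and diary-recorded involvement. The comparison promised in Section 3.2.3.1 cannot be made from what Table 9 schedules, and Section 3.2.6 cannot repair that. The between-group step comparison reads any existing difference in activity as an effect: a moderate assumed gap of 0.5 SD raises the false-positive rate from 5% to about 34%. These rates assume roughly normal outcomes, full follow-up of 30 and 15, and a 5% test. The gap itself is unknown and could be nil. The regression describes an association with self-chosen use, and it understates the effect to an unknown degree if post-use attitudes are adjusted for.

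A reader might go further and infer that no effect of the network can be estimated at all. The documents do not support that. Users have start and end questionnaires, and the group comparison is valid under an assumption of comparable groups. The accurate statement is that the step effect cannot be estimated without that assumption, and that the schedule gives no means of checking or relaxing it. This should be changed before the study starts.

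**What to change.** 1. **Table 9.** Give all 45 participants counters and diaries for 2 weeks before the workshop, as Table 10 already does for the FriWalk study. State that controls complete both the start and the end questionnaire.
2. **Main analysis in Section 3.2.6.** Compare all 30 users with the 15 controls, adjusted for the pre-use value of the same measure. Because allocation is not random, show the change-score and covariate-adjusted results together and say which is primary.
3. **Regression.** Use only pre-use attitude scores as covariates. Report acceptance and engagement as exploratory associations with the outcomes, not as effects of use.
4. **Conclusions.** Describe the group comparison as non-randomised unless allocation is randomised. Randomising would be better still, but it is a larger design change and the other three items do not depend on it.

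The cost is two more weeks of counters and diaries, plus a short start questionnaire for the 15 controls if it is not already intended. No more participants are needed.

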- 10 participants will be used to test the FriWalk to tour the museum.
- 10 participants will be used to have a non-FriWalk based museum tour.
- 10 participants will be selected as a control group (no tour, no FriWalk).

Scales

The objectives listed above provide the conceptual variables that need to be measured. What follows is how we propose to measure them.

Control variables

Each of the control variables are taken from the UTAUT scale (Morris et al. 2003) and the items will be adaptations (for the ACANTO system) of these items. In the case of the social network testing, we will also ask about their engagement with the system to control for participants who were less interested in the system.

Variable	Scale/measure		
Perceived social involvement	Three items asking about the extent of perceived social involvement, its quality, and its enjoyability.		
Actual social involvement	In participant diaries, participants will list who they met during the day from outside the people who live in their home (1 item). This should be corroborated with data from the social network system.		
Quality of recommendations	Several items asking about the personal relevance of the recommendations, the liking of the recommendations, and the ability to do the recommendations.		
Turnout to experimenter- organised event	Number of people who attend event (recorded by experimenter)		
Liking of participants for one another	Several items asking to what extent they perceive others in the group as similar and the extent to which they like them.		
Physical activity	Number of steps taken as measured by step counters		
Well-being	Personal wellbeing index (International Wellbeing Group 2013)		
Perceived sleep quality	Pittsburgh Sleep Quality Index (Buysse et al. 1989)		

Table 7	. Social	l networl	k testing
---------	----------	-----------	-----------

Table	8.	Fri	Walk	testing
-------	----	-----	------	---------

Variable	Scale/measure	
Physical activity	Steps from step counters	
Fear of falling	Falls Efficacy Scale International Short form (Kempen et al. 2008)	
Anxiety about attending event	Several items asking extent to which the user feels anxious about attending events outside the home (baseline) and the extent to which they feel anxious attending events where a FriWalk is available. Anxiety will be asked with reference to (a) finding their way around the environment and (b) having physical support.	

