Test event	To test the system, the experimenters will run an interactive workshop and will advertise it via the ACANTO social network. The topic of this workshop is to be decided, but it may be something like, "A guide to smartphones for the older user." The activity will be tagged with relevant tags (e.g. "technology", "internet") and users who express these interests should receive a recommendation for the workshop. Turnout will be monitored at the event and liking for others in the group will be assessed.	
Return and debrief	After the 2 weeks, all participants will return and be debriefed on the purpose of the study. Additional measures will be taken via a short questionnaire (to see changes from the questionnaire administered at the start of the study).	

Table 10. Phases of FriWalk study

	Phase 1: Ethics, recruitment and collaboration
Ethics	Ensure ethical approval is obtained from UNAN ethics procedure
Recruitment	Recruit interested participants to take part in the FriWalk trial.
Collaboration	Collaboration with museums to implement FriWalk devices in the environment.
	Phase 2: Pilot testing
Testing at UNAN	Devices will be set up on UNAN premises and participants will be invited to try out the devices. Data will be collected about users' average walking pace to assist with matching participants for the museum trial.
Baseline tracking	Participants will be given diaries and step counters to monitor their baseline activity.
	Phase 3: Museum testing
Museum tour start	 Participants will be invited to a tour of a museum where they will be given a FriWalk. Approximately 4 participants will be in each group, assuming that 4 FriWalk devices will be available. Each group will be tested on separate days. Some of these events may be advertised via the social network system. Participants may be matched based on their average walking pace or ability.

Pre-tour questionnaire	Questionnaires will be completed before the tour.
Tour	The tour will involve a programmed route during which the FriWalk will guide the user around the museum. An experimenter will accompany the participants.
Post-tour questionnaire	After the tour, a questionnaire will be completed to ask about the experience.
Control group	A tour will be arranged without the FriWalk and will act as a control group. Questionnaires will be completed before and after.
Second control group	Participants in the no-tour, no-FriWalk group will attend the university to provide answers to a questionnaire.

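### The FriWalk museum comparison in 3.2.6 names no baseline term for its main group contrast, although pre-tour scores and baseline steps are collected and there are only 10 people per group

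*Protocol*

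**What the plan says.** The statistical plan for the social trial (Protocol 3.2.6) assigns ANOVA to both of its studies. For the social-network study it covers "differences between groups in the CPSN (social network users vs. non-users and pre-trial vs. post-trial". For the museum study the matching phrase is "in the FriWalk testing (experimental groups vs control groups", with no pre/post element. The same paragraph adds that the ANOVAs will serve as interaction tests, "to see whether the use of the walker interacts with other measures (e.g. fear of falling or frailty". Regression that controls for other measures is described for use of the social network.

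The museum study has three groups (3.2.3.4, recruitment list for this study). The device arm is given as "10 participants will be used to test the FriWalk to tour the museum". The comparison arm that also takes a tour is given as "10 participants will be used to have a non-FriWalk based museum tour". The third arm is given as "10 participants will be selected as a control group (no tour, no FriWalk". No random allocation to these groups is stated.

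Table 10 sets out what is measured. For the FriWalk tour, "Questionnaires will be completed before the tour", and again afterwards. The non-FriWalk tour group also has questionnaires before and after. The no-tour group attends the university for a questionnaire, and no before/after pair is mentioned. Diaries and step counters record baseline activity. In the device try-out, data are taken on "average walking pace to assist with matching participants for the museum trial". Section 3.2.3.1 adds that fear of falling is measured at baseline. Table 8 lists time to find facilities as a comparison of times between people with and without the FriWalk.

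**The concern.** Several museum outcomes are worded as changes (less fear of falling, more steps, better well-being), and before-values are collected for many of them. The analysis sentence for this study nevertheless names only the group contrast, while the same sentence gives the social-network study a pre/post comparison.

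Two things are at stake. The first is precision: at 10 per group, between-person variation that a baseline score would explain stays in the error term. The second is comparability: without stated random allocation, the groups may differ at the start in fear, anxiety or activity. A contrast of post-tour values carries that difference into the FriWalk estimate. Adjustment removes only the measured part of it.

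**Working it through.** **No stated figure to reproduce.** The museum study gives no power, effect size, SD or sample-size calculation. The check is therefore what 10 per group implies, with and without a baseline covariate.

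**Inputs**
- n = 10 in each tour group (Protocol 3.2.3.4).
- Two-sided 5% level. This is an assumption: 0.05 is stated in 3.1.4 for the clinical trial only.
- True difference d = 0.8 or 1.0 SD (assumed).
- Baseline-outcome correlation ρ = 0.3, 0.5 or 0.7 (assumed).

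**Formulas**
- Unadjusted: noncentrality = d·√(n/2), 18 df.
- ANCOVA, one covariate: residual variance is multiplied by (1 − ρ²), so noncentrality = d·√(n/2)/√(1 − ρ²), 17 df.
- ANCOVA with an allowance for chance baseline imbalance in small groups: variance is multiplied by a further 1 + 1/(2n − 4) = 1 + 1/16.

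**Numbers for d = 0.8**
- Unadjusted: 0.8 × √5 = 1.789; critical t (18 df) = 2.101; power 0.395.
- ρ = 0.5: 1.789/√0.75 = 2.066; critical t (17 df) = 2.110; power 0.495.
- ρ = 0.5 with the allowance: 2.066/√1.0625 = 2.004; power 0.472.

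| Difference | Unadjusted | ρ = 0.3 | ρ = 0.5 | ρ = 0.7 |
|---|---|---|---|---|
| 0.8 SD | 40% | 40-42% | 47-50% | 63-66% |
| 1.0 SD | 56% | 57-60% | 66-68% | 82-84% |

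In each range the lower figure includes the small-sample allowance.

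**In other terms (without the allowance).** The difference detectable with 80% power falls from 1.32 SD to 1.27, 1.15 and 0.95 SD at ρ = 0.3, 0.5 and 0.7. Ten adjusted participants per group carry the information of 10/(1 − ρ²), that is about 11, 13 and 20 unadjusted ones.

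**Walking pace and time to find facilities.** This outcome has no pre-tour value, so it was examined by simulation. Time was taken as distance divided by pace plus search time, with no true wayfinding effect. Every input is assumed: mean pace 0.9 m/s with SD 0.2, distance 50 or 100 m, search-time SD 10 to 40 s.
- Equal expected pace: the unadjusted comparison rejects in about 5% of runs, as it should.
- FriWalk group 0.1 m/s faster: a spurious advantage of about 6 s (50 m) or 13 s (100 m); rejection 6-14%.
- FriWalk group 0.2 m/s faster: about 12 s or 23 s; rejection 9-45%.
- With 1/pace as covariate: mean difference about 0; rejection 4-6%.

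False positives above the nominal level therefore require a systematic pace difference between the groups.

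**The case against.** The best reply is that 3.2.6 is a two-paragraph outline that allows for a variety of methods, and that covariates are often left to a separate analysis plan. Part of this stands: the text does not forbid adjustment. But the Protocol's opening summary says that this document specifies the statistical analysis plan, and 3.2.6 carries that title. Its ANOVA sentence gives one study a pre/post comparison and the other none.

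A second reply is that a baseline does enter some museum models. The planned interaction tests would ordinarily include the measure itself, fear of falling is measured at baseline, and 3.2.3.1 says the control variables apply to the FriWalk as well. This also stands in part. A reader might infer that the museum analysis is a bare between-group ANOVA into which no baseline measure enters; the documents do not support that. What they do leave open is the main group comparison, because an interaction test asks whether the effect varies and does not commit the main contrast to a baseline term.

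A reader might further infer that walking pace will pass for a wayfinding effect. That is not supported either. The documents show no pace difference between groups and foresee matching on pace. The matching is optional, however, and is described where tour groups of about four are formed, so it does not guarantee balance between arms.

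Finally, every power gain rests on an assumed correlation, and some outcomes, such as willingness to return for a FriWalk tour, may have no meaningful pre-tour value. Both points are correct and limit the size and scope of the benefit.

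**Conclusion.** The point holds in a limited form. The main museum comparison is stated without a baseline term, although suitable baselines are collected in both tour groups. At 10 per group this gives up precision, and with no stated random allocation it leaves measured baseline differences in the estimate. The loss is worth recovering if the correlation is about 0.5 or higher: about 8 to 10 points of power at 0.8 SD when it is 0.5. It is slight at 0.3. Even with adjustment at 0.5, power for 0.8 SD does not exceed 50%, so the change improves a small study without making it well powered.

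For time to find facilities, pace imbalance is possible but not established. This is a low-severity improvement, and no stated figure in the Protocol is wrong.

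**What to change.** In 3.2.6, state that FriWalk tour versus non-FriWalk tour is analysed by ANCOVA for every outcome with a baseline: the post-tour score with the same participant's pre-tour score as covariate, and step count with baseline steps. Keep the no-tour group descriptive where it has no matching pre-score. The planned interaction tests can remain as additional analyses.

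For time to find facilities, adjust for Phase 2 walking pace only if it is measured in the same way in both tour groups. The Protocol records pace when participants try out the devices. It does not say whether the non-FriWalk tour group is measured, or whether pace is taken with or without the walker. State this, and state whether any matching on pace is done between arms.

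Cost: a wording change and one degree of freedom per covariate. The questionnaire and step-count adjustments use data already planned; the pace adjustment may need an added measurement in the non-FriWalk tour group.
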